11.2.3 Primary Outcome Measure

Correlation between the number of pre-existing RV-16-specific T cells at Week 15, and infection after homologous re-challenge with RV-16 or infection after heterologous re-challenge with RV-39 at Week 15. With regard to measurement transformation, in our past characterization of T-cell responses to RV-16 and RV-39, we have found that the measurement distribution of many of the aforementioned outcome measures (e.g., T-cell response, viral load) exhibit prominent right-tailed skewness, which depending upon whether a parametric or a non-parametric analysis approach is utilized to analyze the data, has required either rescaling the outcome data to a logarithmic scale (e.g., log₁₀ scale), or rescaling the data to a rank scale, respectively.

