11.3 Sample Size Considerations

11.3.1 Sample Size Calculation Summary

The number of subjects enrolled for initial challenge with RV16 (80) is determined based on power analyses related to the primary outcome measure in Aim 2. In Aim 2, our sample size is designed to address the hypothesis that ***high frequencies of pre-existing RV-16-specific memory T cells directed against conserved epitopes protect against RV-39 infection.*** **Our primary objective is to test the relationship between the frequency of RV-16-specific memory T cells at 15 weeks and viral infection in response to re-challenge with RV-16 or RV-39.** In order to do this, we must first establish that there is a scientifically meaningful reduction in the RV infection rate for secondary versus primary RV challenge. A sample size of 35 volunteers per re-challenge will provide a two-sample test of equal proportions with 85% statistical power (with a one-sided $\alpha=0.025$ type I error rate) to detect a reduction of as small as 28% between the infection rate following primary challenge and the infection rate following secondary challenges.

If we have 35 volunteers per re-challenge, and if the underlying bivariate correlation between the frequency of RV-16-specific memory T cells at 15 weeks and viral infection in response to secondary challenge with RV-16 or RV-39 is at least 0.46 units in absolute magnitude - which if true, would be considered a scientifically meaningful association - we expect to have at least 0.80 statistical power to reject the null hypothesis that there is no correlation between the frequency of RV-16-specific memory T cells at 15 weeks and viral infection in response to secondary challenge with RV-16 or RV-39.

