11.3.2 Power Calculation Details

The “TWO SAMPLE FREQ” statement of the SAS version 9.4 (SAS Institute Inc., Cary, NC) “POWER Procedure” was used to conduct the first portion of the power analysis. As user input, the infection rates for the primary and secondary RV challenges were specified as 0.90 and 0.65, respectively. A zero difference in the infection rates of the primary and secondary RV challenges was specified as the null difference and the alternative difference was specified as a 0.25 unit reduction (i.e., $0.90 - 0.65$) in the secondary RV challenge infection rate compared to the primary challenge infection rate. In accordance with the alternative hypothesis “less than” direction, an $\alpha=0.025$ one-sided type I error rate was specified, and the group sample sizes were specified as $n=80$ for the primary RV challenge and $n=35$ for the secondary RV challenge. Based on this set of input parameters, a sample size of 35 volunteers per re-challenge should provide a statistical test with at least 85% power (with a one-sided $\alpha=0.025$ type I error rate) to detect a reduction of as small as 28% (i.e., $[(0.90-0.65)/0.90 \times 100\%]$) between the infection rate following primary challenge and the infection rate following secondary challenge.

The “ONE CORR” statement of the SAS version 9.4 “POWER PROCEDURE” was used to conduct the second portion of the power analysis. As user input, the null correlation was specified to be zero and the alternative correlation was specified to be 0.46. The test statistic was specified as the “Fishers z statistic”, and the two-sided type I error rate (α) was specified as $\alpha=0.05$. Based on this set of input variables, the power to detect a correlation of 0.46 in absolute magnitude is 0.81.

The rationale for the number of subjects screened is as follows:

- 750 volunteers will be screened for antibody to provide approximately 120 volunteers who are seronegative to both RV-16 and RV-39.
- Of the 120 resulting seronegative volunteers, approximately 96 will have a matched RV tetramer available for the T-cell studies.
- 80 eligible subjects (after review of other inclusion/exclusion criteria) will be challenged with RV-16, approximately 72 (90%) will be infected.
- 70 subjects (35 per virus) will be rechallenged with either RV-16 or RV-39.

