With regard to hypothesis testing, the GEE version of the Wald test will be used to test whether the log-odds for infection is the same for the primary RV-16 challenge and the RV-16/RV-39 re-challenge. The Wald test will also be utilized to test whether the log-odds of infection is the same for the RV-16 and RV-39 re-challenges. For the primary challenge versus re-challenge comparisons, a 0.025 one-side decision rule will be utilized as the null hypothesis rejection criterion, while for the RV-39 re-challenge versus RV-16 re-challenge comparison, a two-sided 0.05 decision rule will be utilized as the null hypothesis rejection criterion. With regard to odds ratio confidence interval construction, the GEE version of Wald confidence interval will be utilized to estimate the lower and upper limits of the 95% confidence interval. The relationship between the number of pre-existing RV-16 specific T-cells (15 wks.) and infection following re-challenge with RV-39, as assessed by virus shedding in nasal lavage, will be quantitatively expressed in terms of the Pearson Product-Moment correlation coefficient if the bivariate normal assumption is deemed creditable based on the observed data, or quantitatively expressed in terms of the Spearman Rank correlation coefficient if the bivariate normal assumption is not supported by the observed data. In either case, the pivotal quantity for the null hypothesis test that the true correlation coefficient is equal to zero will be the Fishers z-statistic, and a two-side $p \leq 0.05$ decision rule will be utilized as the null hypothesis rejection criterion. Confidence interval construction for estimating the underlying correlation coefficient will be based on the Fishers z-transformation method [40].

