With regard to hypothesis testing, the GEE version of the Wald test will be used to test whether the log-odds for infection is the same for the primary RV-16 challenge and the RV-16/RV-39 re-challenge. The Wald test will also be utilized to test whether the log-odds of infection is the same for the RV-16 and RV-39 re-challenges. For the primary challenge versus re-challenge comparisons, a 0.025 one-side decision rule will be utilized as the null hypothesis rejection criterion, while for the RV-39 re-challenge versus RV-16 re-challenge comparison, a two-sided 0.05 decision rule will be utilized as the null hypothesis rejection criterion. With regard to odds ratio confidence interval construction, the GEE version of Wald confidence interval will be utilized to estimate the lower and upper limits of the 95% confidence interval. We will examine potential relationships between RV-16 specific Tfh/Teff cells and post-RV-16/RV-39 challenge infection as assessed by viral load. Bivariate relationships will be quantified either by the Pearson Product Moment correlation coefficient or by the Spearman Rank correlation coefficient. In either case, the pivotal quantity for the null hypothesis test that the correlation coefficient is equal to zero will be the Fishers z-statistic, and a Bonferroni corrected two-sided $p \leq 0.05/c$ decision rule will be used as the null hypothesis rejection criterion, where the “c” represents the total number of null hypothesis tests. Correlation coefficient confidence interval construction will be based on the Fishers z-transformation method. As part of the correlation analysis, we will also compare the correlation coefficients for RV-16 specific Tfh/Teff cells and post-RV-16 challenge viral load relationships to the correlation coefficients for the RV-16 specific Tfh/Teff cells and post-RV-39 challenge viral load relationships by way of *distribution-free* random permutation tests [41], where virus re-challenge type (i.e., RV-16 or RV-39) will be the variable utilized to generate the pseudo null permutation distribution. A Bonferroni corrected two-sided $p \leq 0.05/c$ decision rule will be used as the null hypothesis rejection criterion, where the “c” represents the total number of null hypothesis tests. Cox Proportional Hazards regression will be used to examine multivariate relationships between the pre-challenge RV specific T-cell frequencies and time to RV-16 virus shedding.

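### The stated primary outcome covers re-challenge with RV-16 or RV-39, but section 11.5.2 gives a T-cell test for RV-39 only, so the RV-16 half has no primary test

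*Combined protocol and SAP*

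**What the plan says.** **Both viruses.** The primary objective (3.1.1, repeated in 11.2.1) links RV-16-induced T-cell immunity to the response to either re-challenge virus. The primary outcome (3.2.1, repeated in 11.2.3) correlates Week 15 T-cell numbers with "infection after homologous re-challenge with RV-16 or infection after heterologous re-challenge with RV-39 at Week 15". Section 11.3.1 states the primary objective as concerning "viral infection in response to re-challenge with RV-16 or RV-39", and words its 0.46 correlation power statement the same way. Section 11.3.2 plans that "70 subjects (35 per virus) will be rechallenged with either RV-16 or RV-39".

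**RV-39 only.** The sizing hypothesis in 11.3.1 is that memory T cells "protect against RV-39 infection". The heading of 11.5.2 names RV-39 alone. So does its correlation test, which covers "The relationship between the number of pre-existing RV-16 specific T-cells (15 wks.) and infection following re-challenge with RV-39" by Fisher's z at two-sided 0.05.

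**Where the RV-16 re-challenge group does appear.**
- In 11.5.2 it is one level of the three-level challenge factor in the GEE model of infection rates. That factor is the model's only predictor.
- In 11.5.3, an exploratory section, Tfh/Teff cells are related to "post-RV-16/RV-39 challenge infection as assessed by viral load". A permutation test compares these correlations between viruses, and both are Bonferroni-corrected.
- Section 11.5.3 also has a Cox model for time to RV-16 shedding.
- Section 11.5.1 lists correlations of T-cell numbers with quantitative shedding and time to shedding, without restriction by virus.

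**The concern.** A primary outcome should have an analysis that delivers it. Here the outcome names two re-challenge groups and the analysis section gives the T-cell test for one. Under the plan as written, the 35 volunteers re-challenged with RV-16 do not enter the primary T-cell correlation.

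The plan also does not say how the two viruses relate: jointly required, alternatives, ordered or pooled. If an RV-16 correlation is added at analysis because the outcome definition calls for it, the word 'or' in that definition would let a positive result with either virus be reported as the primary finding. No rule limits the chance of a false claim in that case.

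A related gap concerns order. Section 11.3.1 presents a reduction in infection rate from primary to secondary challenge as something to be established before the T-cell relationship is tested. Section 11.5.2 lists the rate comparison and the correlation test without making one conditional on the other. The reader cannot tell whether a failed rate comparison blocks the T-cell claim.

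**Working it through.** **Inputs.** From 11.3.2, "the null correlation was specified to be zero and the alternative correlation was specified to be 0.46", with Fisher's z and two-sided alpha 0.05. That paragraph does not repeat n, so n = 35 is taken from 11.3.1.

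**1. The plan's own figure.** Power = Φ(√(n − 3) × atanh(r) − z).
- atanh(0.46) = 0.497 and √32 = 5.657; their product is 2.813.
- 2.813 − 1.960 = 0.853, so power = 0.803.
- With the small-sample term r/(2(n − 1)) = 0.46/68 = 0.0068 added to atanh(r), power = 0.814.

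The stated 0.81 is reproduced, for one correlation test in one group of 35.

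**2. Both viruses primary, no adjustment.** The two groups are different people, so the tests are independent under the null. Family-wise error = 1 − 0.95² = 0.0975.

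**3. Alpha split, 0.025 two-sided per virus.** The critical value becomes 2.241.
- 2.813 − 2.241 = 0.572, so power = 0.716 (0.729 with the small-sample term).
- The correlation detectable with 80% power rises from 0.458 to 0.497.
- Keeping 80% power at r = 0.46 needs 42 per group, or 84 re-challenged. At 10% attrition, 84/0.9 = 93.3, so 94 would be challenged first.

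**4. Fixed sequence, RV-39 then RV-16, each at 0.05.** Family-wise error for the two T-cell tests is 0.05. RV-39 keeps its 0.80 to 0.81 power. Power to show both is 0.803² = 0.645 if r = 0.46 in each group (0.814² = 0.66 with the small-sample term).

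**5. All 70 together.** The correlation detectable with 80% power is tanh((1.960 + 0.842)/√67) = tanh(0.342) = 0.33, against 0.458 with 35. This holds only if the correlation is the same for both viruses.

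**6. Whether another planned analysis fills the gap.** The primary outcome pairs T-cell number with culture-defined infection (3.2.1).

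| Analysis with RV-16 re-challenge data | T-cell variable | Outcome | Match |
|---|---|---|---|
| GEE, 11.5.2 | none | infection | no |
| Correlations and permutation test, 11.5.3 | Tfh/Teff cells | viral load | no |
| Cox model, 11.5.3 | T-cell frequency | time to RV-16 shedding | no |
| Correlations listed in 11.5.1 | T-cell number | quantitative shedding, time to shedding | no |

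None is the test that the primary outcome describes.

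**The case against.** The strongest reply is that RV-39 was always the confirmatory question. The sizing hypothesis in 11.3.1 names RV-39, the 11.5.2 heading and test name RV-39, and the power input is a single correlation at two-sided 0.05. On that reading the analysis is right and the objective and outcome are worded too broadly. This is a fair reading and one of the two acceptable resolutions. It does not remove the contradiction, because the next sentence of 11.3.1 names both viruses as the primary objective.

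Two stronger readings are tempting but not supported. A reader might infer that the primary error rate is undefined. It is not: the RV-39 test, taken alone, has a stated two-sided 0.05 criterion, and the 9.75% arises only if both viruses are primary. A reader might also infer that RV-16 re-challenge is ignored, or appears only in a viral-load correlation. It is a level in the 11.5.2 GEE, with Wald tests, and it enters the other analyses listed above.

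It would also be wrong to multiply the power of the rate comparison by that of the correlation and present the product as the study's power. No gate is written into 11.5.2, and both analyses use the same re-challenge infection outcomes, so independence cannot be assumed.

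Finally, 11.2 says that the usual primary and secondary framework does not apply to a mechanistic study. That lowers the stakes. But the plan still names a primary outcome, powers it and sets a rejection rule.

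**Conclusion.** The contradiction stands. The objective, outcome and power statement cover two viruses, the primary T-cell test covers one, and 11.3.1 is split within itself. As written, the RV-16 half of the stated primary outcome has no test.

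In size: one RV-39 test has 5% error and about 0.80 to 0.81 power at r = 0.46. Two unadjusted tests have 9.75% family-wise error. Splitting alpha leaves about 0.72 to 0.73 power per virus.

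These figures assume 35 analysable volunteers per group and use the plan's Fisher-z method, although infection is binary in 3.2.1. The exclusions from analysis in 11.3.2 (positive respiratory panel on the challenge day, or shedding of another rhinovirus) could bring a group below 35.

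**What to change.** **Main change.** In 11.5.2, add the same T-cell/infection correlation test for the RV-16 re-challenge group, performed at two-sided 0.05 only if the RV-39 test is significant. Align 3.2.1, 11.2.3 and 11.3.1 with that order. This needs wording only, uses data already planned and costs RV-39 no power. The price is that any RV-16 claim depends on RV-39 succeeding, with about 0.65 power to show both. The plan should say so.

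**Acceptable alternative.** Declare RV-39 the sole primary test, narrow the objective, outcome and power wording to match, and list the RV-16 correlation as a named secondary test. The choice is the sponsor's.

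**Optional support.** A model on all 70 with T-cell frequency, virus and their interaction may be added as supportive only. The 0.33 figure should not be used to justify it as primary, because it presumes equal correlations after homologous and heterologous re-challenge. At the planning rate of 0.65, about 0.35 × 35 ≈ 12 volunteers per group would be uninfected, so the interaction would be weakly estimated.

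**Order of tests.** State whether the infection-rate comparison is a gate for the T-cell test, so that 11.3.1 and 11.5.2 agree. Either answer is workable.

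Section 15.4 places the outcome analysis after all clinical interventions, so these choices can be fixed before T-cell data are linked to infection results.

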11.5.3 Potential analyses for exploratory endpoints

Infection rates at primary challenge and the infection rates at secondary challenge will be analyzed by way of a binomial generalized estimating equation (GEE) model [37]. The GEE model response variable will be a binary indicator variable that will be assigned the value 1 if the volunteer is deemed infected on RV challenge and the value 0 will be assigned otherwise. The GEE model predictor variable will be 3 level classification variable. One level will differentiate the primary RV-16 challenge outcome data from the secondary RV challenge outcome data, a second level will identify the secondary RV-16 challenge outcome data, and the third level will identify the secondary RV-39 challenge outcome data. Since we expect that approximately 90% of the volunteers who undergo the primary RV-16 challenge will be eligible to undergo either RV-16 or RV-39 re-challenge, we cannot legitimately assume that the primary challenge infection status and re-challenge infection status of the volunteers who undergo re-challenge are statistically independent. To account for possible *intra-subject* measurement correlation, the components of the GEE model variance and covariance matrix will be estimated by the Huber and White sandwich estimator [38, 39].

With regard to hypothesis testing, the GEE version of the Wald test will be used to test whether the log-odds for infection is the same for the primary RV-16 challenge and the RV-16/RV-39 re-challenge. The Wald test will also be utilized to test whether the log-odds of infection is the same for the RV-16 and RV-39 re-challenges. For the primary challenge versus re-challenge comparisons, a 0.025 one-side decision rule will be utilized as the null hypothesis rejection criterion, while for the RV-39 re-challenge versus RV-16 re-challenge comparison, a two-sided 0.05 decision rule will be utilized as the null hypothesis rejection criterion. With regard to odds ratio confidence interval construction, the GEE version of Wald confidence interval will be utilized to estimate the lower and upper limits of the 95% confidence interval. We will examine potential relationships between RV-16 specific Tfh/Teff cells and post-RV-16/RV-39 challenge infection as assessed by viral load. Bivariate relationships will be quantified either by the Pearson Product Moment correlation coefficient or by the Spearman Rank correlation coefficient. In either case, the pivotal quantity for the null hypothesis test that the correlation coefficient is equal to zero will be the Fishers z-statistic, and a Bonferroni corrected two-sided $p \leq 0.05/c$ decision rule will be used as the null hypothesis rejection criterion, where the “c” represents the total number of null hypothesis tests. Correlation coefficient confidence interval construction will be based on the Fishers z-transformation method. As part of the correlation analysis, we will also compare the correlation coefficients for RV-16 specific Tfh/Teff cells and post-RV-16 challenge viral load relationships to the correlation coefficients for the RV-16 specific Tfh/Teff cells and post-RV-39 challenge viral load relationships by way of *distribution-free* random permutation tests [41], where virus re-challenge type (i.e., RV-16 or RV-39) will be the variable utilized to generate the pseudo null permutation distribution. A Bonferroni corrected two-sided $p \leq 0.05/c$ decision rule will be used as the null hypothesis rejection criterion, where the “c” represents the total number of null hypothesis tests. Cox Proportional Hazards regression will be used to examine multivariate relationships between the pre-challenge RV specific T-cell frequencies and time to RV-16 virus shedding.

We will examine potential relationships between the levels of RV-16- and RV-39-specific antibodies and illness (i.e., total symptom score on day of peak symptom) following heterotypic re-challenge with RV-39, as well as potential relationships between the levels of RV-16- and RV-39-specific antibodies and illness following homotypic re-challenge with RV-16. Bivariate

relationships will be quantified either by the Pearson Product-Moment correlation coefficient or by the Spearman Rank correlation coefficient. In either case, the pivotal quantity for the null hypothesis test that the true correlation coefficient is equal to zero will be the Fishers z-statistic, and a Bonferroni corrected two-sided $p \leq 0.05/c$ decision rule will be implemented as the null hypothesis rejection rule, where the c represents the total number of null hypothesis tested. Correlation coefficient confidence interval construction will be based on the Fishers z-transformation method. As part of analysis, we will also compare the correlation coefficients for the relationships between RV-16- and RV-39-specific antibodies and illness following heterotypic re-challenge with RV-39 to the correlation coefficients for the relationships between RV-16- and RV-39-specific antibodies and illness following homotypic re-challenge with RV-16 by way of distribution free random permutation tests [40], where virus re-challenge (i.e., heterotypic or homotypic) will be the variable utilized to generate the pseudo null permutation distribution. A Bonferroni corrected two-sided $p \leq 0.05/c$ decision rule will be used as the null hypothesis rejection criterion, where the “ c ” represents the total number of null hypothesis tests.

Pre and post-RV-16-specific Tfh/Teff cells frequencies and pre- and post-challenge RV-16- and RV-39-specific antibody frequencies will be analyzed via linear mixed effects models. For each outcome variable, the linear mixed model will be specified to include a single fixed-effect, which will identify the outcome assessment time (i.e., pre- or post-RV-16 challenge), and a single random effect that will identify the subject. Based on our prior work, we anticipate that the majority of these outcomes variables will have to be analyzed on the \log_{10} scale to reduce the impact of right tailed distribution skewness, and hence, the pre- to post-change in the response will be quantified as a ratio (post:pre) of geometric means. The pivotal quantity for hypothesis testing will be the “linear-contrast of means” t-statistic, and a two-sided $p \leq 0.05$ decision rule will be utilized as the rejection criterion for testing the null hypothesis that there is no underlying pre- to post-challenge change in the mean/geometric mean of outcome distribution.

The longitudinal clinical outcome data such as viral load, cytokine concentration, and cold symptom scores, that will be collected on the day of RV inoculation (i.e., day 0) and on post-challenge days 1, 2, 3, 4, and 5 will be analyzed via linear mixed models (e.g., cytokine response) and via generalized estimating equation models (e.g., total daily symptom score). The linear mixed models and generalized estimating equation models will be specified so that the longitudinal response profiles of the secondary challenges can be compared with the longitudinal response profiles of the primary challenge. With regard to hypothesis testing, all statistical tests will be two-sided and a Bonferroni corrected $p \leq 0.05/c$ decision rule will be implemented as the null hypothesis rejection criterion, where c denotes the number of between-challenge comparisons.

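### The exploratory test families in 11.5.3 use single-step Bonferroni; Holm's step-down procedure keeps the same 0.05 familywise level and never rejects less (an efficiency point, not an error)

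*Combined protocol and SAP*

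**What the plan says.** Section 11.5.3, headed "Potential analyses for exploratory endpoints", states a Bonferroni rule five times:

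- For the correlations of RV-16-specific Tfh/Teff cells with viral load, the test is based on the "Fishers z-statistic, and a Bonferroni corrected two-sided" threshold of 0.05/c, where c "represents the total number of null hypothesis tests".
- The permutation tests that compare those correlations between the two re-challenge viruses use the same rule.
- For the correlations of antibody level with illness, the threshold "will be implemented as the null hypothesis rejection rule, where the c represents the total number of null hypothesis tested".
- The permutation tests that compare those antibody correlations between homotypic and heterotypic re-challenge use it again.
- For the day 0 to 5 longitudinal models, "all statistical tests will be two-sided and a Bonferroni corrected" threshold applies, "where c denotes the number of between-challenge comparisons".

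No number is given for c, no step-down procedure is mentioned, and no reason is given for the single-step form. The Fisher z confidence intervals for the correlations carry no adjusted level. The primary correlation (11.5.2) and the pre/post mixed models (11.5.3) are tested at an uncorrected two-sided 0.05, so this point does not reach them.

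**The concern.** Single-step Bonferroni compares every p-value in a family with 0.05/c, however many others have already been rejected. Holm's procedure orders the p-values and compares the smallest with 0.05/c, the next with 0.05/(c−1), and so on, stopping at the first failure. Its first threshold is Bonferroni's and every later one is larger. So it cannot lose a Bonferroni rejection, and it controls familywise error at 0.05 under any dependence between the tests.

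At stake is power in a small study. The only power figure that the plan gives for a correlation (11.3.2) is for one test at 0.05. None is given at 0.05/c, where power is lower. If several effects in a family are real, which is plausible under the hypothesis in 11.1 that both Th and Tfh cells protect, the single-step rule leaves some of them undetected for no gain in the familywise guarantee.

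**Working it through.** **Inputs from the documents.** n = 35 per re-challenge virus; r = 0.46 as the meaningful correlation; Fisher z test; stated power 0.81 at two-sided 0.05 (11.3.1, 11.3.2). Rule p ≤ 0.05/c (11.5.3).

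**Assumptions.** c = 2, 4, 8 or 20; the share of real effects in a family; r = 0.46 for each real effect; normally distributed test statistics, independent or correlated 0.5.

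**Step 1: the plan's own figure.** Power = Φ(atanh(r)·√(n−3) − z), ignoring the negligible opposite tail. Here atanh(0.46) = 0.4973, √32 = 5.657, and their product is 2.813. With z = 1.960, power = Φ(0.853) = 0.803. Adding the bias term r/(2(n−1)) = 0.46/68 to atanh(r) gives 0.814. The stated 0.81 reproduces.

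**Step 2: the same correlation at 0.05/c** (no bias term).

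| c | z | 2.813 − z | Power |
|---|---|---|---|
| 2 | 2.241 | 0.572 | 0.716 |
| 4 | 2.498 | 0.316 | 0.624 |
| 8 | 2.734 | 0.079 | 0.531 |
| 20 | 3.023 | −0.210 | 0.417 |

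**Step 3: Holm against Bonferroni**, 100,000 simulated families per setting, independent tests. Each cell gives per-hypothesis power, Bonferroni → Holm, with the share of families in which Holm rejects more hypotheses in brackets.

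| c | All real | Half real | A quarter real |
|---|---|---|---|
| 2 | 0.717 → 0.779 (12%) | 0.716 → 0.718 (2%) | – |
| 4 | 0.623 → 0.731 (35%) | 0.625 → 0.651 (6%) | 0.626 → 0.627 (1%) |
| 8 | 0.532 → 0.651 (56%) | 0.531 → 0.564 (13%) | 0.533 → 0.542 (3%) |
| 20 | 0.417 → 0.499 (73%) | 0.416 → 0.443 (24%) | 0.418 → 0.429 (6%) |

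With statistics correlated 0.5 the picture is similar. At c = 8, power goes from 0.531 to 0.639 if all are real and from 0.532 to 0.563 if half are.

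**Step 4: error control.** Holm never rejected fewer hypotheses than Bonferroni in any setting, and its simulated familywise error never exceeded 0.05. With half the effects real and independent tests, familywise error went from 0.024 to 0.038 (c = 4), 0.025 to 0.036 (c = 8) and 0.024 to 0.031 (c = 20). Both methods made at least one rejection in exactly the same data sets, as they must, because both require the smallest p-value to be at most 0.05/c.

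**Not computed.** The permutation tests compare two correlations, and the longitudinal models compare challenges. No power gain was worked out for either.

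**The case against.** The strongest reply is that nothing here is wrong. Bonferroni is valid, the analyses are exploratory, 11.2 says that the usual primary and secondary outcome framework does not apply, and the primary correlation is untouched. That stands: this is a choice between two valid methods.

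A second reply is that Holm's extra power is not free. Bonferroni also bounds the expected number of false rejections at 0.05; Holm does not. In a simulation with c = 12, half the effects real and r = 0.5, expected false rejections rose from 0.031 to 0.047. This is a fair qualification. It is not decisive, because 11.5.3 states no error goal beyond dividing 0.05 by c, whose ordinary purpose is familywise control, and Holm keeps that.

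A third reply is practical. Section 15.4 describes laboratory work as iterative, and Holm needs all the p-values of a family before its later steps. But the same section places outcome analysis after all clinical interventions are complete, so ranking is feasible. What stands is that c must be fixed first, and the text does not make clear whether c is counted per family or over all exploratory tests.

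A fourth reply is that Fisher z is approximate for rank correlations. With independent predictors and no real effects, simulated familywise error at n = 35 was about 0.06. That is the same for both methods and gives no reason to prefer either.

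Bonferroni is sometimes kept for its matching simultaneous confidence intervals. That defence is not available here, because the plan's intervals carry no adjusted level.

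**Conclusion.** The point holds as a low-cost improvement to a valid rule. That Holm never rejects less, at the same familywise level, is a mathematical result for valid p-values and needs no assumption about c or dependence. The size of the gain does need assumptions, because the documents do not give c or the number of real effects. For zero-correlation tests at n = 35 and r = 0.46 with c of 4 to 20, it is 8 to 12 points of per-hypothesis power if all effects are real, about 3 points if half are, and 0 to 1 point if a quarter are.

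Three stronger readings are not supported:

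- A reader might infer that Holm will often yield more findings. That is so only when many effects in a family are real; with a quarter real, extra rejections occur in about 1% to 6% of families. Holm never turns a family with no finding into one with a finding.
- A reader might infer that correlation between immune readouts on the same volunteers drives the gain. Holm makes no use of that correlation; its gain comes from several hypotheses being rejected together.
- A reader might carry these figures over to the permutation or longitudinal families. Holm's dominance applies there too, but no size has been established.

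**What to change.** In 11.5.3, replace the p ≤ 0.05/c rule in all five places by Holm's procedure within the same families: order the c p-values, compare the i-th smallest with 0.05/(c−i+1), and stop at the first that fails. Add a short list that names each family and its c, fixed before that family's p-values are ranked, and say whether c is counted per family or overall.

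The cost is five small text edits and that list. No data, volunteers or confidence intervals are affected, the primary analysis does not change, and no Bonferroni rejection can be lost. The price is that Holm uses more of the nominal 0.05 and that a family's results cannot be finalised until all its p-values are available.
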